## LIST OF ABBREVIATIONS

ACRONYM	DESCRIPTION
ACT	Acceptance and Commitment Therapy
CAAQ	Cancer Acceptance and Action Questionnaire
CPAQ	Chronic Pain Acceptance Questionnaire
CRP	Cancer Related Pain
EHR	Electronic Health Record
IIT	Investigator-Initiated Trial
IRT	Item Response Theory
PROMIS	Patient-Reported Outcome Measurement Information System
SF-36	Medical Outcomes Study 36-Item Short Form Health Survey
TAU	Treatment as Usual

## PROTOCOL SUMMARY / SYNOPSIS

**Protocol Title:** *Acceptance and Commitment Therapy for Chronic Pain in Cancer Survivors*

- Objectives:**
- **Primary Objective:**  
*To evaluate the feasibility, acceptability, and fidelity of implementing of an 8-week, group-based, Acceptance and Commitment Therapy (ACT) intervention for chronic pain management in cancer survivors who have completed active treatment.*
  - **Secondary Objectives:**  
*To evaluate preliminary clinical efficacy of an 8-week, group-based, ACT intervention for chronic pain management in cancer survivors who have completed active treatment.*
- Endpoint:**
- **Primary Endpoint:**  
*The primary implementation outcomes are feasibility, acceptability, and fidelity. Following completion of the intervention, semi-structured qualitative interviews with intervention group members will be used to assess participant acceptability of the ACT intervention content, complexity and credibility, as well as patients' perspectives on intervention delivery. Additionally, weekly rating forms using Likert scales to collect quantitative data will be used to assess acceptability of content for each individual group therapy session. Feasibility will be evaluated through the collection of participant enrollment and adherence data throughout the intervention period and follow-up. Fidelity of the treatment will be measured through observation and the use of standardized checklist of core intervention components*
  - **Secondary Endpoints:**  
*The secondary clinical efficacy outcomes are physical and emotional functioning as measured by the SF-36. Implementation outcomes will include acceptability, feasibility, and fidelity..*
  - **Tertiary/exploratory:**  
*Tertiary/exploratory outcomes include pain interference and pain intensity as measured by instruments from the National Institute of Health's Patient-Reported Outcomes Measurement Information System (PROMIS) and psychological flexibility (chronic pain and cancer specific) as measured by The Chronic*

[figure not shown]
*Pain Acceptance Questionnaire and The Cancer Acceptance and Action Questionnaire.*

- Population:**
- **Sample size:**
    - Maximum number of participants that can be enrolled is 140
    - Minimum number of participants to be enrolled 50 (number of participants needed to answer feasibility aim)
  - **Gender:** Male and Female
  - **Age Range:** 18-100
  - **Demographic group:** Ambulatory outpatient oncology
  - **General health status:** Chronic pain,  $\geq$  three months since active treatment (e.g., chemotherapy, radiation, surgery)
  - **Geographic location:** University of Colorado Cancer Center

**Number of Participating Sites enrolling participants:** 1 (University of Colorado Cancer Center)

**Study Duration:** 3 years

## SCHEMATIC OF STUDY DESIGN

## 1 PARTICIPATING SITES

A complete and current listing of investigators, research personnel, research facilities and other study centers (if applicable) participating in this study will be maintained throughout the duration of this study

## 2 INTRODUCTION: BACKGROUND INFORMATION AND SCIENTIFIC RATIONALE

### 2.1 BACKGROUND INFORMATION

As the number of cancer survivors in the United States grows, so too does the occurrence of chronic, cancer-related pain conditions. Combinations of surgical treatment, radiation, and chemotherapy can contribute to various chronic pain syndromes in cancer survivors that can last long after active treatment has ended. It is estimated that nearly 40% of cancer survivors experience cancer-related pain (CRP) following completion of active treatment [1].

Five and ten year cancer survival rates have shown a consistent increase [2], shining a light on the long-term effects of cancer treatment, including chronic CRP. It has been recommended that treatment guidelines for chronic CRP mirror those already established for other chronic pain conditions, which often recommend a holistic approach facilitating pain relief as well as rehabilitation [3, 4]. Behavioral treatments are a key component to this approach, including psychological interventions, which have shown significant positive effects on pain severity and interference during treatment [5, 6]. Until recently, research for CRP has focused on procedure-related pain or pain during active treatment. There is relatively little intervention data on pain management following active treatment, creating a gap in the literature regarding strongly supported behavioral treatments for CRP in extended survivorship [6]. Applying efficacious pain management interventions from other chronic pain populations, assessing their effectiveness in chronic CRP, and evaluating their implementation are important next steps in this area of survivorship care.

Acceptance and Commitment Therapy is a theory-based treatment approach included under the broader Cognitive Behavioral Therapy umbrella. The core therapeutic process of ACT is psychological flexibility – the ability to continue in value-based behavioral engagement or change despite the presence of difficult sensations or cognitions. Acceptance and Commitment Therapy has been shown to be efficacious as an intervention for non-cancer chronic pain, specifically on outcomes of pain acceptance, psychological flexibility, functioning, anxiety, and depression [7, 8]. Acceptance and Commitment Therapy has also been shown to be feasibly delivered in cancer survivor populations for a variety of outcomes including quality of life [9, 10], disease related distress [11] and anxiety [12], and lifestyle change [13]. Though ACT has been used as an intervention for other types of pain management and with cancer populations, it has yet to be investigated as an effective and feasible treatment for survivors with chronic CRP. As the number of cancer survivors grows, addressing this chronic, disease-related issue will become a critical piece of providing high-quality cancer survivorship care.

## 2.2 RATIONALE

Until recently, research for CRP has focused on procedure-related pain or pain during active treatment. There is relatively little intervention data on pain management following active treatment, creating a gap in the literature regarding strongly supported behavioral treatments for CRP in extended survivorship. Applying efficacious pain management interventions from other chronic pain populations, assessing their feasibility and efficacy in chronic CRP are important next steps in this area of survivorship care.

**Aim 1: To evaluate the implementation of an 8-week, group-based, Acceptance and Commitment Therapy (ACT) intervention for chronic pain management in cancer survivors who have completed active treatment.**

**Implementation outcomes will include acceptability, feasibility, and fidelity.** Following completion of the intervention, semi-structured qualitative interviews with intervention group members will be used to assess participant acceptability of the ACT intervention content (e.g., complexity and credibility), as well as patients' feedback on intervention delivery. Additionally, weekly rating forms using Likert scales to collect quantitative data will be used to assess acceptability of content for each individual group therapy session. Feasibility will be evaluated through the collection of participant enrollment and adherence data throughout the intervention period and follow-up. Fidelity of the treatment will be measured through observation and the use of standardized checklist of core intervention components.

**Aim 2: To evaluate the preliminary clinical efficacy of an 8-week, group-based, Acceptance and Commitment Therapy (ACT) intervention for chronic pain management in cancer survivors who have completed active treatment.**

Participants (n = up to 140) will be randomly assigned to an ACT intervention and treatment as usual (TAU) or TAU alone. The ACT intervention will include eight weekly group sessions that will assist patients in developing skills to accept unhelpful internal events in order to clarify values and promote engagement in committed behaviors. The TAU condition will include medication management as directed by prescribing provider (e.g., physician), as well as access to Cancer Center supportive oncology services and other provider recommendations (e.g., acupuncture).

- **Changes in physical and emotional functioning** in the intervention group will be compared to the control group over time. The primary outcomes are physical and emotional functioning as measured by the SF-36. We hypothesize that improvements in physical and emotional functioning will occur in both groups over time but will be greater for the intervention group at completion of the program and at six and 12-week follow-ups as compared to the TAU group.

**Aim 3: To conduct exploratory analyses on pain interference, pain intensity, and psychological flexibility (chronic pain and cancer specific), which have been identified in the literature as secondary outcomes and process outcomes of ACT in chronic pain.**

- **Changes in pain interference, pain intensity, and psychological flexibility (chronic pain and cancer specific)** will be compared over time as exploratory outcomes between the intervention group and the TAU group. We hypothesize that improvement in these variables will occur in both groups over time but will be greater in the intervention group at completion of the program and at six and 12-week follow-ups.

## 2.3 POTENTIAL RISKS AND BENEFITS

### 2.3.1 KNOWN POTENTIAL RISKS

There are minimal risks to study participants. However, the ACT intervention, as well as measures included in assessment for all participants, will ask participants to reflect on both physical and psychological constructs that may be related to their cancer experience. This may result in distress. In the event that distress is acute, psychosocial support will be available for all participants. It is the expectation that participants in both groups will experience some benefit from active pain management intervention. All ACT groups will be directed by a licensed clinical psychologist in order to monitor for any distress in the group. Additionally, assessments of emotional functioning and pain experience (i.e., interference and severity) will be measured at the midpoint of the intervention in order to assess for any possible iatrogenic effect. These measures are precautionary in nature as there are no known potential risks for this intervention.

### 2.3.2 KNOWN POTENTIAL BENEFITS

The risks to participants are reasonable in relation to the anticipated benefits to participants and/or society, and in relation to the importance of the knowledge that may reasonably be expected to result, thereby falling in favor of performing the study:

- To Participant: This intervention has been found to improve functioning in non-cancer chronic pain populations. We hypothesize that it will also be effective with this sample.
- To Society: Effective and feasible behavioral interventions for chronic pain management are critical in order to meet the need for supportive care in our growing population of cancer survivors.
- Justify the importance of the knowledge gained: Improving our understanding of chronic pain management in cancer survivors and the feasibility of delivering the intervention will inform future research regarding symptom management in this population as well as direct clinical care in the field of psycho-oncology.

## 3 OBJECTIVES AND PURPOSE

- **Primary objective:** To evaluate the implementation of an 8-week, group-based ACT intervention for chronic pain management in cancer survivors who have completed active treatment.
- **Secondary objective:** To evaluate the preliminary clinical efficacy of an 8-week, group-based ACT intervention for chronic pain management in cancer survivors who have completed active treatment.

## 4 STUDY DESIGN AND ENDPOINTS

### 4.1 DESCRIPTION OF THE STUDY DESIGN

This study is a single site (University of Colorado Cancer Center), randomized control trial. It will investigate the implementation (i.e., feasibility, acceptability, and fidelity) and preliminary clinical efficacy of an ACT intervention plus TAU for chronic pain in cancer survivors compared to TAU alone. Following consent, participants will provide baseline data including demographic and clinical characteristics. Participants will be randomized to ACT plus TAU or TAU alone. Due to study design, it is not possible to blind either participants or investigators to study condition. Participants will complete assessments at baseline, 4-week intervention midpoint, 8-week intervention completion, 6-week follow-up, and 12-week follow-up.

### 4.2 STUDY ENDPOINTS

#### 4.2.1 PRIMARY ENDPOINT

Implementation outcomes will include acceptability, feasibility, and fidelity. Following completion of the intervention, semi-structured qualitative interviews with intervention group members will be used to assess participant acceptability of the ACT intervention for management of chronic pain and value-based behavioral engagement. Additionally, weekly rating forms using Likert scales to collect quantitative data will be used to assess acceptability of content for each individual group therapy session. Feasibility will be evaluated through the collection of participant enrollment and adherence data throughout the intervention period and follow-up. Fidelity of the treatment will be measured through observation and the use of standardized checklist of core intervention components.

#### 4.2.2 SECONDARY ENDPOINTS

Changes in physical and emotional functioning in the intervention group will be compared to the control group. The primary outcomes are physical and emotional functioning as measured by the

SF-36. We hypothesize that improvements in physical and emotional functioning will occur over time in both groups, but will be greater for the intervention group at completion of the program and at six and 12-week follow-ups as compared to the control group. The SF-36 has been used in previous studies evaluating ACT and chronic pain [14, 15]. Furthermore, the use of physical and emotional functioning as primary endpoints directly aligns with the theoretical basis of acceptance-based therapies [15].

#### 4.2.3 EXPLORATORY ENDPOINTS

Tertiary/exploratory outcomes include pain interference and pain intensity as measured by the National Institute of Health's PROMIS measures and psychological flexibility (chronic pain and cancer specific) as measured by The Chronic Pain Acceptance Questionnaire and the Cancer Acceptance and Action Questionnaire, respectively. These constructs have been previously supported as secondary outcomes and process outcomes of ACT in chronic pain populations [14, 15].

### 5 STUDY ENROLLMENT AND WITHDRAWAL

#### 5.1 PARTICIPANT INCLUSION CRITERIA

In order to be eligible to participate in this study, an individual must meet all of the following criteria:

1. Provision to adhere to the consent form and verbally consent
2. Stated willingness to comply with all study procedures and be available for the duration of the study
3. Be a male or female aged 18-100
4. Have pathology confirmed diagnosis of a solid tumor cancer
5. Be three or more months out from active cancer treatment (surgery, chemotherapy, and/or radiation)
6. Endorses experiencing pain for three or more months prior to eligibility screening
7. Indicates moderate to severe difficulties with pain interference as related to their cancer experience, with a score of 4 or higher on the pain interference item from the Chronic Pain Grading Questionnaire
8. Shows no evidence of cancer disease (NED) or with stable, chronic disease under “watchful waiting”
9. Fluent in English
10. Psychiatric stability as assessed by chart review and study personnel (e.g., not exhibiting symptoms consistent with diagnoses of serious mental illness such as active psychosis or mania)
11. Ability to meet remotely via internet connection or over the phone.

## 5.2 PARTICIPANT EXCLUSION CRITERIA

An individual who meets any of the following criteria will be excluded from participation in this study:

1. Having pain that can be solely attributed to a diagnosis outside of their cancer experience
2. Presenting with barriers to group participation (e.g., social anxiety) or when group-based provision of care would impede participant's treatment or that of other group members
3. Patients with a diagnosis of malignant neoplasm of the brain (ICD-10 C71) or malignant neoplasm of spinal cord, cranial nerves and other parts of central nervous system (ICD-10 C72).

## 5.3 STRATEGIES FOR RECRUITMENT AND RETENTION

We will recruit participants from the University of Colorado Cancer Center. Recruitment will occur through a multipronged approach including direct advertisement to patients in the cancer center, as well as targeted recruitment based on cohort discovery through TriNetX and screening of the electronic health record (EHR)/EPIC, including use of the *Slicer Dicer* application.

*Direct patient advertisement.* Direct advertisement to patients will occur in the form of posted fliers and verbal advertisement at patient events (i.e., support groups). Participants will be provided with study information as well as research staff contact information, and they may contact research staff to express interest in participation. Staff will be available to discuss the study further with participants either in person or via telephone and will engage in eligibility screening if appropriate.

*Electronic health record recruitment.* Cohort discovery for feasibility will occur initially through TriNetX. Specifically, our initial cohort count will include patients with diagnoses of both a malignant neoplasm (see Table 1 for example codes) and relevant pain diagnoses (e.g., ICD-10 code G89.3- neoplasm related pain, ICD-10 code G62.0-chemotherapy induced neuropathy). In order to ensure a comprehensive list of relevant ICD-10 disease codes we will confer with clinical disease site co-investigators, CU Medicine billing, and/or EPIC resources. Following Institutional Review Board approval, this cohort will then be identified for further screening of eligible criteria by research staff using both TriNetX and EPIC review in concert with the use of its application *Slicer Dicer*. Other institutional research databases approved by COMIRB may also be utilized for recruitment purposes. Disease site clinic leaders will be included as co-investigators for optimized clinical collaboration and recruitment. MRNs and PIDs will be used to create a key, and then screen participants in EPIC using this key. The study team will retain this key in a separate file from the main database until data collection is complete. Participants found to be eligible following EHR screening will initially be contacted via mail or email with information regarding the study. Mailings to patients will be sent on behalf of both the study PI and clinic director for the patient's relevant disease site. Participants will have the opportunity to "opt out" of further contact by study staff by contacting a provided telephone number.

Participants who do not choose to opt out will be contacted by research staff for further evaluation of interest in study participation and eligibility screening if appropriate.

Research staff will have a total of 3 independent points of contact with the patient, including the initial letter/email and two follow-up telephone calls. If possible, voicemail messages will be left at both follow-up telephone calls. This does not include points of contact from the research staff that are dependent on participant initiation of communication (i.e., calling a patient back after they have left a message). After receiving the letter/email and two telephone calls, the patient will no longer be contacted by research staff unless upon participant request.

## 5.4 PARTICIPANT WITHDRAWAL OR TERMINATION

### 5.4.1 REASONS FOR WITHDRAWAL OR TERMINATION

Participants are free to withdraw from participation in the study at any time upon request. An investigator may terminate participation in the study if any clinical adverse event (AE) or other medical or psychological condition or situation occurs such that continued participation in the study would not be in the best interest of the participant.

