#### **5.4.2 HANDLING OF PARTICIPANT WITHDRAWALS OR TERMINATION**

Participants will be informed in the consent process that they may discontinue the study at any time.

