### **5.5 PREMATURE TERMINATION OR SUSPENSION OF STUDY (STUDY STOPPING RULES)**

As stated above, the anticipated risks of participating in this study are low. Should study PI ([name]) believe at any point in the study that participation is detrimental to the participant's health, they will end the subject's participation and refer the subject to other relevant treatment resources as appropriate (i.e., mental health resources).

If, after three consecutive months of active recruitment and enrollment, investigators are unable to sufficiently recruit patients to conduct a single intervention group, consideration of an alternative design (i.e., multiple baseline single arm) will be considered. Following modification of design due to low enrollment, if after three consecutive months of active recruitment and enrollment investigators are unable to sufficiently recruit patients to conduct a single intervention group, the trial will be considered not feasible for implementation and terminated.

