### 7.2.5 EARLY TERMINATION VISIT

If the participant chooses to terminate participation early, he or she will be contacted either in person or by phone to verify the decision to discontinue the study.

---

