#### 8.1.1 DEFINITION OF ADVERSE EVENTS (AE)

The following are considered to be adverse events:

- Increase in symptoms of depression and/or anxiety directly related to the act of participating in the intervention (i.e., scheduling appointments, additional visits).
- Increase in symptoms of depression and/or anxiety directly related to material presented in the intervention or the focus groups.
- Increases in anxiety and/or depression related to cancer diagnosis, treatment, impact of treatment on functioning and treatment side effects are **not** considered adverse events.

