#### **10.3.4 ADHERENCE AND RETENTION ANALYSES**

Feasibility is a key outcome of the implementation aim for this study. Participant eligibility, enrollment, and completion of study intervention and assessments will be tracked through standardized databases (e.g., screening and enrollment). We will also track completion of assessment measures through REDCap. Percentages for each relevant domain will be calculated. Individuals who do not complete assessment time points as prescribed will be contacted by research staff in order to minimize missing data. Participants who choose to withdraw from the study will be contacted to confirm their decision and will be asked why they are choosing to discontinue participations (e.g., time, medical issues, does not feel intervention is helpful). This information will be used to inform future studies and relevant grant applications.

---

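### Sections 5.4.1 and 5.5 end study participation as a whole when continuing is judged harmful, with no written step of stopping ACT but keeping the SF-36 surveys: a cheap improvement

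*Combined protocol and SAP*

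**What the plan says.** **Ending participation.** Section 5.4.1 is permissive. It begins "An investigator may terminate participation in the study if any clinical adverse event (AE" and extends to any other "medical or psychological condition or situation occurs such that continued participation in the study would not be in the best interest of the participant". Section 5.5 is mandatory: should the principal investigator "believe at any point in the study that participation is detrimental to the participant's health, they will end the subject's participation", with referral to other care. Both act on the study as a whole.

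**Handling of those who leave.** Section 5.4.2, whose title promises the handling rules, has one sentence: "Participants will be informed in the consent process that they may discontinue the study at any time". Under section 7.2.5, someone who chooses to stop early is told of no further surveys; "he or she will be contacted either in person or by phone to verify the decision to discontinue the study". Section 10.3.4 adds: "Participants who choose to withdraw from the study will be contacted to confirm their decision and will be asked why".

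**Those who stay.** Section 7.1 and section 7.2.3 have all participants complete every assessment. Section 7.2.6 offers make-up sessions, and section 10.3.4 has staff contact anyone who misses an assessment, to limit missing data. Nothing makes non-attendance a reason for leaving the study.

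**Safety and outcome.** Section 8.1.1 lists as an adverse event an "Increase in symptoms of depression and/or anxiety directly related to material presented in the intervention or the focus groups". Section 2.3.1 says that emotional functioning and pain "will be measured at the midpoint of the intervention in order to assess for any possible iatrogenic effect". Section 10.2 names an intention-to-treat dataset. Section 10.3.3 uses listwise deletion or Full Information Maximum Likelihood (FIML), depending on how much is missing and on whether completers and non-completers differ demographically.

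**The concern.** In this trial the safety signal and an efficacy outcome measure much the same thing. The adverse event of interest is depression or anxiety caused by the intervention. The SF-36 emotional well-being scale, as section 7.1 describes it, asks about nervousness and calm. A participant removed for that distress then contributes no later SF-36 scores (Week 8, 6-week and 12-week), although this is the person whom the iatrogenic check is meant to inform.

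If the exit is explained by a score already recorded, such as Week 4, FIML can use that score. If it follows from distress seen in a session or reported at an adverse-event inquiry, and no recorded score reflects it, FIML does not fully correct the loss. The scores lost would tend to be the poor ones, so the ACT mean would look better than it should. At stake is the between-arm comparison of SF-36 functioning, which is the secondary objective. Feasibility, acceptability and fidelity are not affected.

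**Working it through.** **1. What the text settles.** There are three ways to stop ACT:
- Missing or stopping sessions: surveys continue (7.1, 7.2.3, 10.3.4).
- Termination by the investigator: participation ends (5.4.1, 5.5), and no later survey is described.
- Withdrawal on request: the contact confirms the decision and asks why (7.2.5, 10.3.4). No survey-only option is described, and the consent form, which might contain one, is not visible.

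The gap is therefore limited to the second and third routes.

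**2. Inputs from the plan (10.4, Aim 2).** d = 0.61; pre-post correlation 0.5; 30% attrition; maximum 140, so 70 per arm at 1:1. The attrition allowance is consistent: 92 / 0.70 = 131.4, or 132, within 140. The plan does not split the 30% by reason or arm, so the share leaving by a formal route is unknown.

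**3. Assumed inputs.** p = share of the ACT arm that exits selectively, 2% to 15%. ρ = latent correlation, in a threshold model, between tendency to exit and the outcome given baseline, 0 to 0.5. All other attrition is random, and there is no such loss in TAU. Neither range comes from the documents.

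**4. Formula.** Bias in the ACT mean under FIML, in SD units:

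bias = ρ × √(1 − 0.5²) × φ(z_p) / (1 − p)

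Here z_p is the normal quantile cutting off p, φ is the normal density, and √0.75 = 0.866.

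| p | Of 70 | φ(z_p) | Bias, ρ = 0 | ρ = 0.3 | ρ = 0.5 |
|---|---|---|---|---|---|
| 2% | 1.4 | 0.0484 | 0 | 0.013 | 0.021 |
| 3% | 2.1 | 0.0680 | 0 | 0.018 | 0.030 |
| 10% | 7 | 0.1755 | 0 | 0.051 | 0.084 |
| 15% | 10.5 | 0.2332 | 0 | 0.071 | 0.119 |

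Example at p = 15%, ρ = 0.5: 0.5 × 0.866 × 0.2332 / 0.85 = 0.119.

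**5. How strong ρ = 0.5 is.** The exiters' shortfall below what baseline predicts is ρ × 0.866 × φ(z_p) / p, which is 0.76 SD at 10% and 0.67 SD at 15%. This is a strong form of selection.

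**6. Effect of a recorded Week 4 score.** With all correlations 0.5, the residual SD falls from 0.866 to √(2/3) = 0.816. If ρ = 0.5 still holds for what remains, the bias is 0.080 at 10% and 0.112 at 15%. Week 4 helps little unless it captures the reason for leaving.

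**7. Loss in TAU.** With p = 5% and ρ = 0.5 in TAU, the bias there is 0.5 × 0.866 × 0.1031 / 0.95 = 0.047. The net for ACT 15% against TAU 5% is 0.119 − 0.047 = 0.072. Equal loss gives zero.

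**8. What the fix recovers.** Suppose half of the exiters keep the surveys, at ρ = 0.5. If random attrition brings total loss to 30% before the fix and falls only on the non-exiters, the share of them observed is 0.70 / (1 − p), and

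bias = 0.5 × 0.866 × φ(z_p) × [0.70 / (1 − p) − 0.5] / (0.70 + 0.5p)

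This gives 0.028 at 10% and 0.042 at 15%. If the retained exiters suffer the same random attrition, the figures are 0.040 and 0.055. If no one agrees to continue, nothing changes.

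**The case against.** **Most of the ground is already covered.** Someone who simply stops attending remains on the survey schedule and is chased for missed assessments. This stands, and it confines the point to formal exits.

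**Consent is unseen.** A reader might infer that people who withdraw are never offered a survey-only option. The documents do not support that. Section 5.4.2 points to the consent process, and the consent pages are not available. What can be said is that the protocol sections which should carry the option do not.

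**Ending everything can be right.** Section 2.3.1 says the measures themselves may cause distress, and section 5.4.1 does not compel termination. Both points stand, so the lesser step should be an offer and not a requirement. Section 8.3 follows events until resolution or stabilisation, but that does not supply SF-36 scores.

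**Few such exits are expected.** Sections 2.3.1 and 5.5 describe the risks as minimal or low. A reader might take the 10% to 15% rows as a forecast of safety-driven exits. Nothing in the documents supports that for a low-risk intervention; those rows are conceivable only if all formal routes are pooled. The 2% to 3% rows suit the safety route better, though they too are assumed.

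**Small against sampling error.** With 49 per arm (140 less 30%, halved) and correlation 0.5, the standard error of the adjusted difference is √(2 × 0.75 / 49) = 0.175 SD. The 15% top end is about 0.7 of that. At the minimum of 50 less 30%, or 17.5 per arm, the standard error is 0.29 SD. This stands and keeps the priority low.

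**Direction is not certain.** A reader might also infer that ACT must lose more participants this way. Section 5.4.1 covers other medical or psychological conditions as well, and these can arise in TAU. Greater loss in ACT is possible, because adverse events are defined by the intervention, but it is not shown.

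**Conclusion.** The point holds as a cheap improvement. As written, a participant formally ended for distress has no route to further SF-36 scores, in a dataset described as intention-to-treat, and FIML repairs this only where a recorded score explains the exit. The effect may be zero. With ρ between 0 and 0.5 and no such loss in TAU, the ACT mean is flattered by 0 to about 0.03 SD if 2% to 3% of the arm exits selectively. That is at most about 5% of the planning effect (0.030 / 0.61). Only at 10% to 15% by all formal routes does the top end reach 0.08 to 0.12 SD, or up to about 19% (0.119 / 0.61). The exit shares and ρ are assumptions; 0.61 and 0.5 are the plan's own. The consequence is limited to the secondary, preliminary efficacy aim.

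**What to change.** In sections 5.4.1, 5.4.2, 5.5 and 7.2.5, distinguish:
- (a) ending ACT sessions, whether by the participant's or the investigator's decision;
- (b) withdrawing from assessments.

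Participants in (a) stay enrolled and are offered the scheduled surveys by REDCap, or by phone or paper where section 7.2.3 allows. The exceptions are those who decline and those for whom the assessments themselves are judged harmful. They are analysed in the arm to which they were randomised. The existing exit contact asks about (a) and (b) and records them separately. Who should stop therapy, and when, stays with the investigator.

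The cost is a short protocol amendment, consent wording if the form does not already cover it, and some follow-up contact with people who have left the groups. No design figure changes. The gain depends on how many of them agree to continue.
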